3.3.2 Total Number of Study Sites/Total Number of Subjects Projected

Study site: Neonatal/infant intensive care unit at the Children's Hospital of Philadelphia.

Up to 103 infants will be enrolled in the study to produce up to 52 evaluable subjects (phase 1 trial + observational cohort). These numbers are estimated according to the enrollment flow diagram shown in **Figure 7**. Up to 26 infants are expected to receive the study drug to produce up to 24 infants with evaluable trial data. These numbers for the phase 1 trial account for the 24 infants needed to enroll up to 6 infants per each of the 4 evaluated doses (assuming 1 infant with a toxic response per dose level) plus withdrawal of up to 2 infants (~10%) prior to receiving *14 drug doses* for reasons other than a toxic response. We will target a minimum of 12 infants in the observational cohort. Enrollment in the observational (non-treated) cohort will be capped at 28 infants.

[figure not shown]

Figure 7. Flow diagram of estimated maximum enrollment numbers

3.4 Study Population

3.4.1 Inclusion Criteria

1. Male or female infants born <32 weeks' gestation

- 2. Diagnosed with BPD (use of supplemental oxygen or respiratory support at 36 weeks postmenstrual age)
- 3. Postmenstrual age ≥36 weeks at study enrollment
- 4. Treatment with invasive mechanical ventilation at enrollment without planned tracheal extubation within 7 days after enrollment
- 5. Tracheal aspirate culture positive for a pathogenic GNR bacteria (see list of eligible organisms in section 3.4.3) within 7 days of beginning the study phase this testing will be performed during the screening phase and must be met to participate in the phase 1 trial or observational cohort
- 6. Parental/guardian permission (informed consent).

3.4.2 Exclusion Criteria

- 1. Serum creatinine >0.4mg/dL within 14 days of enrollment
- 2. Congenital or acquired disease of the kidney or renal collecting system that adversely affects renal function
- 3. Congenital or acquired hepatobiliary disease that adversely affects liver function
- 4. Treatment with a systemic antibiotic within 7 days prior to enrollment
- 5. Treatment with a potentially nephrotoxic medication (see list in Appendix A), excluding diuretics, within 48 hours prior to enrollment
- 6. Treatment with a continuous infusion of a neuromuscular blocker (see list in Appendix B) within 48 hours prior to enrollment
- 7. Known intolerance to aminoglycoside antibiotics
- 8. Current treatment with high frequency or other oscillating mechanical ventilation
- 9. Presence of a cancer diagnosis
- 10. Maternal family history of early onset hearing loss defined as the need for an assistive hearing device prescribed before 30 years of age
- 11. Endotracheal tube leak >20%.
- 12. Any investigational drug use (as part of an FDA approved IND protocol) prior to enrollment.
- 13. A subject who, in the judgement of the Investigator, is not an appropriate candidate for this research study.

Subjects that do not meet all of the above criteria may not be enrolled. Any violations of these criteria must be reported in accordance with IRB Policies and Procedures.

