Study Phases						
Screening Phase	Potential subjects will be screened using daily census logs and the protocol inclusion and exclusion criteria. Infants who meet study eligibility criteria will be enrolled if a parent or guardian consents to once-weekly collections of a screening tracheal aspirate culture. If a screening culture is positive for a pathogenic GNR, the infant will be eligible to participate in the phase 1 trial or observational (non-treated) cohort, but can be enrolled in only one.					
Study Phase Phase 1 Trial	The phase 1 trial will last up to 14 days, with each infant receiving a specified dose of tobramycin solution for inhalation every 12 hours, administered via vibrating mesh nebulizer. The drug dose (78mg, 150mg, 216mg, or 300mg) will be determined as per the interpatient dose escalation 3+3 design protocol. If the 300mg dose level is completed without evidence of safety concerns (i.e., stopping rules are not met), up to 3 additional infants will be enrolled to receive 300mg to provide a more robust assessment of drug dose tolerability and PK. During the trial, each infant will undergo continuous pulse oximetry, and blood and tracheal aspirate sampling and respiratory mechanics measurements at prespecified time points to assess dose safety and potential efficacy. Clinical data will also be recorded daily throughout the trial.					
Observational (non- treated) Cohort	Infants enrolled in the untreated observational cohort will undergo continuous pulse oximetry for 14 days after enrollment. Respiratory					

	mechanics measurements will be performed at set timepoints. Clinical data will be collected daily from the medical record.							
Follow-Up Phase	All infants enrolled in the phase 1 trial and observational cohorts will be followed until hospital discharge. Pre-defined clinical data will be abstracted periodically from the medical record. For infants enrolled in the phase 1 trial, tracheal aspirate samples for high resolution culture, 16s sequencing, and cytokine level measurement will be collected ≤48 hours and 14 days after receiving the final dose of inhaled tobramycin. Infants enrolled in the observational cohort will undergo tracheal aspirate collection f culture ≤48 hours after completing the 14-day study phase. Infants in both cohorts will undergo respiratory mechanics measurements ≤48 hours after completing the study phase.							

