3.4.3 Definition of Pathogenic GNR Airway Bacteria

One or more of the following pathogenic GNR organisms must be cultured from a tracheal aspirate sample within 7 days prior to enrollment to meet trial eligibility:

- Pseudomonas aeruginosa
- Klebsiella species
- Enterobacter species
- Stenotrophomonas maltophilia
- Escherichia coli
- Acinetobacter baumannii
- Serratia marcescens

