The American Academy of Pediatrics (AAP) recommends that all infants at risk of hearing loss should undergo subsequent screening by 24 to 30 months of age. Importantly, recommendations for audiologic follow-up should be customized based on individual patient risk factors and likelihood of delayed-onset hearing loss. Accordingly, the Joint Committee on Infant Hearing (JCIH) recommend beginning in 2019 that that all infants with a risk indicator for hearing loss who pass the initial newborn hearing screen should be referred for an audiologic assessment by 9 months of age.⁸⁶

Owing to challenges of completing audiologic testing in preterm infants who are receiving intensive care (e.g., ongoing invasive mechanical ventilation) and obstacles that contribute to obtaining these tests in this population (infants with severe BPD in the CHOP N/IICU require a median of 3 attempts at audiology screening before a test can be successfully performed – regardless of the eventual result), all audiologic screening in study participants will be performed prior to hospital discharge as per standard of care in the CHOP N/IICU. All study infants will undergo pre-discharge ABR and OAE testing as well as tympanometry as indicated by the audiologic evaluation. The results of these evaluations will be recorded as part of the study data. The rate of failed pre-discharge hearing tests in a recent cohort of infants who received care in the CHOP N/IICU and were similar to those eligible for this study was 36%.⁸⁷ Based on these data, a rate of pre-discharge hearing screening abnormalities ≥50% among the infants treated with inhaled tobramycin will trigger adverse event reporting to the IRB and FDA. In addition, the rates of failed pre-discharge audiometric evaluations will be compared between infants who participate in the

investigational drug trial and those who are enrolled in the study but do not participate in the drug trial (e.g., lack of GNR in the airway or parental refusal to participate in the phase 1 trial). A statistically significant difference in the rates of failed evaluations between these two groups will also trigger adverse event reporting to the IRB and FDA.

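### *Enrollment* has two incompatible meanings, so the eligibility windows that count from it need not reach the first tobramycin dose

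*Combined protocol and SAP*

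**What the plan says.** Four exclusions in section 3.4.2 look back from enrollment:

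- creatinine: "Serum creatinine >0.4mg/dL within 14 days of enrollment" (the abstract and synopsis count back from enrollment)
- systemic antibiotics: "Treatment with a systemic antibiotic within 7 days prior to enrollment"
- nephrotoxic drugs: "Treatment with a potentially nephrotoxic medication (see list in Appendix A), excluding diuretics, within 48 hours prior to enrollment"
- neuromuscular blockers: "Treatment with a continuous infusion of a neuromuscular blocker (see list in Appendix B) within 48 hours prior to enrollment"

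Inclusion criterion 4 in section 3.4.1 looks forward 7 days from the same point for a planned extubation. None of these windows counts from the first dose. Criterion 5, the positive culture, counts from the start of the study phase.

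The synopsis (Screening Phase) says when an infant becomes enrolled: "Infants who meet study eligibility criteria will be enrolled if a parent or guardian consents to once-weekly collections of a screening tracheal aspirate culture". Section 3.4.3 says the organism "must be cultured from a tracheal aspirate sample within 7 days prior to enrollment to meet trial eligibility". Table 1 marks the inclusion and exclusion review once, in the Screening column, with no mark on Day 0 or Day 1.

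**The concern.** These windows keep recent renal, antibiotic and paralytic exposure away from the start of tobramycin. The protocol's own evidence is about drug start, not consent. Section 1.6.1.2 describes a kidney-injury case with intravenous gentamicin within 48 hours of starting inhaled tobramycin, and section 1.6.2.2 bases the blocker exclusion on co-treatment.

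The primary endpoint includes two creatinine rises and a urine-output criterion. A renal effect of another drug given in the gap could therefore be scored as a toxic response, and under section 5.2.5 more than one such response at a dose level stops the study. Colony-count change, measured from the screening culture, would also absorb any systemic antibiotic given in the gap.

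**Working it through.** The plan gives no figure to reproduce. The check compares the uses of the word and then does date arithmetic.

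**1. Two meanings.**

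- *Screening consent.* The synopsis says so directly. Section 3.3.2 uses the word the same way: "Up to 103 infants will be enrolled in the study to produce up to 52 evaluable subjects". So does section 5.2.3, which compares hearing results with "those who are enrolled in the study but do not participate in the drug trial" and counts infants without a Gram-negative rod among them.
- *Cohort entry.* Section 3.4.3 puts the positive culture before enrollment. Section 3.4.2 closes by barring enrollment of anyone who fails any criterion. Criterion 5 cannot be met at screening consent, so section 3.4 must mean a later point. Sections 3.1.1, 9.5 and 9.6 also speak of enrolling into a cohort or dose level.

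**2. What the 103 counts.** Evaluable infants: 24 + 28 = 52, as stated. Infants entering a cohort: 26 + 28 = 54. Section 9.5 gives 54-60% of infants culture-positive, so 54 / 0.54 = 100 or 54 / 0.60 = 90 would need screening. The stated 103 is close to 100, which is consistent with counting infants consented to screening. Figure 7 is not visible, so its steps cannot be confirmed.

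**3. Gap if enrollment is cohort entry.** Consent precedes study procedures (section 4.1), and research oximetry starts 24-48 hours before the drug (sections 3.1.2 and 4.3.4). Enrollment is therefore at least about 24 hours before dose 1. The study period must begin within 7 days of collecting the positive sample (section 3.1.1), so the gap g is at most about 7 days. A look-back of length W covers max(0, W − g) of the same length of time before dose 1:

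| Window | g = 1 day | g near 7 days |
|---|---|---|
| 48 h nephrotoxin or blocker | 48 − 24 = 24 h covered | 0 (already 0 at g = 48 h) |
| 7-day antibiotic | 7 − 1 = 6 days covered | about 0 |
| Oldest look-back creatinine at dose 1 | 14 + 1 = 15 days | 14 + 7 = 21 days |
| Planned extubation, days left after dose 1 | 7 − 1 = 6 | about 0 |

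The last row matters because section 4.7.2 replaces infants who leave for non-safety reasons before 14 doses. At 12-hour intervals, 14 doses take 7 days.

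**4. Gap if enrollment is screening consent and nothing is re-checked.** Days from first sample to dose 1 ≤ 7k + 7, where k is the number of negative weekly cultures. Any delay from consent to the first sample is extra. The value of k is an assumption, since the protocol sets no cap.

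| k | Gap, up to (days) | Oldest creatinine, up to 14 + gap (days) |
|---|---|---|
| 0 | 7 | 21 |
| 1 | 14 | 28 |
| 2 | 21 | 35 |
| 3 | 28 | 42 |

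If eligibility is re-checked at each weekly culture, the gap falls back to at most about 7 days after the positive sample.

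**5. What else could cover the gap.** Section 4.7 withdraws trial subjects who start an intravenous antibiotic or a blocker infusion. Section 5.2.4 stops infants prescribed a systemic antibiotic after commencing the trial. Both look forward from trial participation, and neither names other Appendix A drugs, such as ibuprofen, enalapril or the contrast agents.

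**6. Baseline creatinine.** Tables 1 and 5 schedule the first study metabolic panel on Day 1, after dose 2. The pre-trial value must come from elsewhere and may predate an exposure in the gap. With the maximum eligible baseline of 0.4 mg/dL, the fold criterion is crossed above 1.5 × 0.4 = 0.60. From an illustrative 0.2 it is crossed above 0.30. Small rises are enough.

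**The case against.** The strongest reply is that section 3.4 can only mean cohort entry, for the reason in step 1, and that the synopsis sentence is loose wording. Sections 3.1.1 and 4.1 continue screening only while the infant remains eligible, and section 3.2 allocates drug to infants who satisfy the criteria and have phase 1 consent. The natural reading is continuing reassessment. Table 1 also reviews medications and laboratory results on Day 0 and every trial day, and exclusion 13 lets the investigator decline an unsuitable infant. Finally, the creatinine criteria are rises above a pre-trial value, so a stable elevation would not count.

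Much of this stands. It removes any claim that infants go unobserved for weeks, and it makes the multi-week gap an upper bound. It does not close the shorter gap. The continuing-eligibility wording gives no date, procedure or re-anchored window. The Day 0 reviews are not tied to eligibility, and Day 0 may itself fall up to 7 days before Day 1. If phase 1 consent already counts as trial participation, section 4.7 covers intravenous antibiotics and blocker infusions started in the gap, but not other Appendix A drugs. The rise-above-baseline argument depends on when the baseline was drawn: an old value turns a rise within the gap into an apparent drug effect.

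**Conclusion.** The point holds as an inconsistency with a practical consequence. Under either meaning of enrollment, no criterion requires a clear window up to the first dose. The uncovered interval is about 24 hours to about 7 days if enrollment is cohort entry. It is up to 7 + 7k days if enrollment is screening consent, cultures are exactly weekly and eligibility is not re-checked.

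Three stronger readings are not supported:

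- *That the protocol defines enrollment as screening consent, leaving weeks unprotected.* Section 3.4.3 contradicts this, and the continuing-eligibility text points the other way.
- *That repeat screening will be common among treated infants because 40-46% are not culture-positive.* The 54-60% in section 9.5 is per infant. Infants who never turn positive are never dosed, and the documents give no distribution of the number of cultures.
- *That false toxic responses will stop the trial.* The documents give no rate of exposure in the gap or of renal events from it. The route to a false stop exists, but its probability cannot be estimated.

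**What to change.** Reconcile the synopsis Screening Phase text, sections 3.1.1, 3.2, 3.4.1, 3.4.2 and 3.4.3, and Table 1, so that one explicitly named event anchors all five windows. The window lengths are for the sponsor to decide. Use a different term for consent to screening if the 103 is meant to count those infants.

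Add a row to Table 1 for a documented eligibility re-check by chart review immediately before dose 1 (trial) or study day 1 (observational cohort). A mark on Day 0 alone would not do this, because Day 0 can be a week early. State which creatinine result is the pre-trial value and record its date.

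The cost is protocol wording and one chart check per infant. A few infants may be deferred or found ineligible, which could slow accrual slightly.

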3.4.3 Definition of Pathogenic GNR Airway Bacteria

One or more of the following pathogenic GNR organisms must be cultured from a tracheal aspirate sample within 7 days prior to enrollment to meet trial eligibility:

- Pseudomonas aeruginosa
- Klebsiella species
- Enterobacter species
- Stenotrophomonas maltophilia
- Escherichia coli
- Acinetobacter baumannii
- Serratia marcescens

4 STUDY PROCEDURES

Below is a summary of the study procedures that will occur in each study phase. A list of main study procedures can also be found in **Table 1** (page xiv).

4.1 Screening Phase

Census documents in the CHOP N/IICU will be reviewed bi-weekly during the study period to identify potentially eligible subjects. For subjects likely to be eligible, medical records will be reviewed using the inclusion and exclusion criteria. Study participation and enrollment criteria will first be discussed with the subject's attending physician. After obtaining approval of the attending physician, the parent(s) or guardian(s) will be approached, and the details of the study will be discussed. First, consent will be obtained to collect a screening tracheal aspirate culture up to once weekly for as long as eligibility is maintained and a pathogenic Gram-negative rod organism is not identified. The parent or guardian will be informed that the results of the tracheal aspirate culture(s) will be used to determine eligibility for the phase 1 trial of inhaled tobramycin and the observational cohort. Details of the two study cohorts will be discussed during the initial consent conversations. However, a second consent discussion for participation in the inhaled tobramycin trial or observational (nontreated) cohort will take place for those in whom the tracheal aspirate culture is positive for a pathogenic GNR. After learning of the study goals, procedures, risks and benefits, the parent(s) of eligible infants will be invited to participate in the phase 1 trial or observational cohort and if interested, informed consent will be obtained. Informed consent will be obtained prior to any study related procedures being performed. All screening culture results will be disclosed to families of enrolled infants. See section 9.6 for a description of the informed consent procedure.

4.2 Observational (non-treated) cohort

The medical record of each infant enrolled in the observational cohort will be reviewed regularly until hospital discharge to collect pre-specified clinical data. Each infant in the observational cohort will also undergo respiratory mechanics measurements on study days 1, 7 and \leq 48 hours after completing the 14-day study period (see section 4.3.3). A tracheal aspirate for culture will also be collected \leq 48 hours after completing the 14-day study period (see section 4.3.2). Oxygen saturation data (SpO₂) will be recorded using continuous pulse oximetry. To collect this data, a research pulse oximeter will be placed in addition to the pulse oximeter used for clinical monitoring. This second device will enable reliable data collection, storage, and analysis. Nursing and medical staff will be instructed to use the clinical oximeter for all clinical monitoring.

4.3 Phase 1 Trial of Tobramycin Solution for Inhalation

The phase 1 trial of inhaled tobramycin will utilize a 3+3 inter-patient dose escalation design (**Figure 8**). The safety and tolerability of up to 4 different doses of tobramycin will be evaluated: 78mg, 150mg, 216mg, and 300mg. Each dose will be administered every 12

hours for up to 14 days via vibrating mesh nebulizer. If the 300mg dose level is completed in 3 participants and none show evidence of a toxic response, up to 3 additional infants will be enrolled to receive to receive 300mg. The trial will be stopped if 2 of the additional infants receiving 300mg develop a toxic response and the 216mg dose will be used as the maximum tolerated dose in subsequent trials. The study procedures utilized to monitor drug safety and efficacy are listed in **Table 5**.

[figure not shown]

Figure 8. 3+3 dose escalation design schematic. *MTD: maximum tolerated dose*

4.3.1 Blood draws

All blood samples required as part of this research protocol will be collected by heel stick, venipuncture, or from an indwelling catheter (e.g., arterial line) by nursing staff or CHOP phlebotomy, in adherence with standardized, written hospital guidelines. Samples will then be transferred to the CHOP clinical or research laboratories for analysis. Required blood sample volumes per laboratory test are: serum tobramycin level (0.5mL), comprehensive metabolic panel (1mL), PK blood samples (200µL). In addition to the pre-specified study blood draws, 200µL of blood will be collected for PK analyses on up to 6 different occasions during the phase 1 trial at the times of clinically ordered blood draws. In total, the amount of blood drawn for this study will not exceed 9.1mL over the 14-day study period. This amount of blood extraction is not expected to incur risk to the study patients. As an additional step to protect the safety of enrolled subjects, study team members, in consultation with nursing staff and the medical team, will ensure blood volume extraction (for clinical + research purposes) does not exceed the maximum allowable weight-based limits specified by local and NIH guidelines (no more than 5 mL/kg drawn in a single day).

	0ª	Study Day						Follow-up	
Procedure		1	4	7	10	14	All (1-14)	15 [⊳]	28 ^C
Tracheal aspirate	x		X – after 7 th dose	X – after 14 th dose				х	x
Test:									
Quantitative culture	Х							Х	Х
Cell count differential	Х							Х	Х
Cytokine levels	Х			Х				х	Х
16s sequencing	Х			Х				Х	Х
Tobramycin level ^d			Х	5X	х	Х			
Blood draw		X – after 2 nd dose	X – after 7 th dose	X – after 14 th dose	X – after 20 th dose	X – after 28 th dose			
Test:									
Tobramycin trough ^e		Х	Х	х	х	Х			
Comprehensive metabolic panel ^f		х	х	х	х	х			
Tobramycin peak ^g				х					
Random tobramycin levels ^h							х		
Continuous pulse oximetry	х						х		
Pulmonary mechanics measurements	х			х				х	
Daily medical record review							х		
Weekly medical record review ⁱ								х	х

Table 5. Study procedures utilized to monitor drug safety, tolerability, and efficacy for participants in the phase 1 trial.

^a "Day 0" procedures to be completed ≤7 days prior to administration of the first study drug dose. The quantitative tracheal aspirate culture and cell count differential obtained during the screening phase will be used for the laboratory values. Prior to initiating study drug therapy, one additional tracheal aspirate will be collected for cytokine level measurements and 16s sequencing.

^b "Day 15" procedures to be completed ≤48 hours after administration of the last study drug dose

° Follow-up tracheal aspirate for quantitative culture will be collected 14 days after the last administered dose of inhaled tobramycin or on the day of planned tracheal extubation if earlier

^d Tracheal aspirate for tobramycin level measurements obtained on trial day 7 will be collected approximately 1hr, 3hr, 6hr, 9hr, and 11hr after drug administration. Samples collected on trial days 4, 10, and 14 will be collected approximately 11hr after administration of doses number 8, 20 and 28, respectively.

e Serum and blood tobramycin trough levels will be drawn concurrently, 11 hours after administration of the previous dose

^f Blood draws for comprehensive metabolic panels should be bundled with draws for tobramycin trough levels or other clinically ordered blood draws. Comprehensive panel to include a magnesium and phosphorus level on day 7 and 14.

^g Serum and blood tobramycin peak levels will be drawn concurrently, 1 hour after completion of the previous dose

^h Up to 6 blood tobramycin levels per infant will be drawn concurrent with clinically ordered blood draws.

ⁱ Weekly medical record review to assess for adverse events will take place until hospital discharge

